### **15.3.1.4 Spleen Size Assessment**

Spleen size will be measured by ultrasound. The captured images are recorded and assessed, according to the clinic's routine criteria. Detailed instructions for procedures will be provided in the laboratory manual.

### **15.3.1.5 Hospital Anxiety and Depression Scale (HADS)**

The Hospital Anxiety and Depression Scale (HADS) will be used. HADS is a self-report questionnaire commonly used by doctors and therapists to assess levels of anxiety and depression in patients. The HADS comprises 14 statements which the patient rates based on their experience over the past week. Each question has 4 possible responses. Responses are scored on a scale from 3 to 0. The maximum score is 21 for depression and 21 for anxiety. A score of 11 or higher indicates the probable presence of mood disorder, with a score of 8 to 10 being just suggestive of the presence of the respective state. The HADS is divided into four ranges: normal (0-7), mild (8-10), moderate (11-15) and severe (16-21) (Snaith 2003). HADS was found to perform well in assessing the symptom severity and identifying cases of anxiety disorders and depression in both somatic, psychiatric and primary care patients and in the general population (Bjelland et al. 2002). HADS is being used and confirmed to be a valid tool for assessment of psychiatric side effects of interferon alpha (Kraus et al. 2005). Furthermore, the HADS can be administered by non-psychiatrist physicians (Olsson, Mykletun, and Dahl 2005). For HADS see Appendix 8.

### **15.3.2 Assessment of Safety**

Assessment of safety will be determined by vital signs, clinical laboratory tests, physical examinations, ECGs, heart ECHOs, lung X-rays, ECOG performance status, ocular examinations, and AEs.

### **15.3.3 Subject Demographics and Medical History**

Demographic information (e.g., age, sex, race) will be recorded at screening in the appropriate eCRF. Relevant medical history, including history of prior and current disease(s), and information regarding underlying diseases will also be recorded at screening. Included will be the usage of any and all drugs used to treat PV.

At screening, in-depth medical history data will be collected, including thrombosis/hemorrhage history, *JAK2* mutation status, acquired von Willebrand disease in the past, presence of progressive/symptomatic splenomegaly, symptomatic thrombocytosis, progressive leukocytosis, progressive disease-related symptoms, and vasomotor/microvascular disturbances not responsive to aspirin.

### **15.3.4 Physical Examination**

Information about the physical examination must be present in the source documentation at the study site. The physical examination will include general status, lungs, cardiovascular system, abdomen, musculoskeletal system, skin, lymph nodes, and central nervous system. Any significant findings associated with clinical signs or symptoms, or requiring therapy before the screening visit should be recorded. Clinically significant findings made after the start of the study drug that meet the definition of an AE must be recorded as AEs.

### **15.3.5 Vital Signs**

Body temperature, blood pressure, and pulse rate will be measured after resting in a supine position for 5 minutes at all visits.

### **15.3.6 Electrocardiograms**

In accordance with the study flowchart (Appendix 1), standard 12-lead ECGs will be performed at screening, and prior to study drug administration (0 hr) at Weeks 0, 2, 4, 12, 24, 28, 36, and 52, as well as at early withdrawal and the safety follow-up visit. At Weeks 0 and 28, an additional ECG assessment will be performed at 96 ( $\pm 24$ ) hr after study drug administration. The ECG should be performed following the subject is in a supine position for 5 minutes and prior to the collection of any PK samples.

The QT/QTcF interval will be determined from at least 3 to 5 cardiac cycles (heart beats).

Any abnormal findings assessed by the Investigator as clinically significant should be recorded in the relevant eCRF modules (e.g., AE, medical history).

### 15.3.7 Bone Marrow Assessment

Bone marrow sampling is optional. However, if bone marrow is collected, the following process will be followed. The bone marrow samples should be centrally assessed. Two bone marrow samplings (one at the first study drug dose [Week 0] and one at Week 52) will be taken and sent for central evaluation.

The definition of bone marrow histological remission is disappearance of hypercellularity, trilineage growth (panmyelosis) and absence of > grade 1 reticulin fibrosis.

### 15.3.8 Ocular Examination

All subjects will have an ocular examination at screening and at the EoT visit. The examination will consist of visual acuity assessment, slit lamp examination, tonometry, and fundus examination. Clinically relevant ophthalmological disorder (due to diabetes mellitus or hypertension) at screening will be an exclusion criterion. In addition to scheduled examinations, an ophthalmologist consultation is mandatory for all subjects reporting worsening vision or visual symptoms. P1101 treatment will be discontinued in subjects who develop a new ophthalmologic disorder during the study.

### 15.3.9 Lung X-Ray and Heart ECHO

All subjects will have a lung X-ray and heart ECHO at screening and at the EoT visit. For screening, lung X-rays will be accepted which are not older than 12 weeks prior to the date of screening visit. In case of premature discontinuation, no X-ray examination (but the heart ECHO only) will be performed (to reduce the burden from exposure to radiation) unless necessary for safety follow-up purposes.

Subjects with clinically relevant pulmonary infiltrates, pneumonia, and pneumonitis at screening will not be eligible for the study. In cases of persistent or unexplained pulmonary infiltrates or pulmonary function impairment, treatment will be discontinued as a precautionary measure if deemed necessary in the judgement of the Investigator or sponsor.

### 15.3.10 ECOG Performance Status

The ECOG Performance Status are scales and criteria used by doctors and researchers to assess how a subject's disease is progressing, assess how the disease affects the daily living abilities of the subject, and determine appropriate treatment and prognosis.

The performance status will be assessed according to the ECOG performance status scale as noted in [Appendix 4](#). The ECOG performance status is graded on a 6-point scale (range 0 to 5): 0=Asymptomatic (fully active, able to carry on all pre-disease activities without restriction); 1=Symptomatic but completely ambulatory (restricted in physically strenuous activity but ambulatory and able to carry out work of a light or sedentary nature, e.g., light housework, office work); 2=Symptomatic, <50% in bed during the day (ambulatory and capable of all self-care but unable to carry out any work activities. Up and about more than 50% of waking hours); 3=Symptomatic, >50% in bed, but not bedbound (capable of only limited self-care, confined to bed or chair 50% or more of waking hours); 4=Bedbound (completely disabled, cannot carry on any self-care, totally confined to bed or chair); and 5=Death.

In accordance with the study flowchart (Appendix 1), the ECOG will be performed at screening, and Weeks 0, 12, 24, 36, and 52 following first study drug administration, as well as at early withdrawal/EoT and the safety follow-up visit.

### 15.3.11 Adverse Events

Information regarding occurrence of AEs will be captured throughout the study. Duration (start and stop dates and times), seriousness, severity/grade, outcome, concomitant medication use, action taken, and relation to study drug will be recorded in the eCRF. For more information on safety reporting, see [Section 16](#).

### 15.3.12 Laboratory Evaluations

Table 15-1 presents the list of clinical laboratory measurements that will be performed. A local laboratory will be used for analysis of all specimens. Hematology specimens for baseline (Visit 1) and Months 3, 6, 9, and 12 will also be evaluated by the central laboratory. Details on the collection, shipment of samples, and reporting of results will be provided to Investigators in the laboratory manual. For the schedule of the laboratory assessments, refer to Appendix 1, Appendix 2 and Appendix 3.

**Table 15-1 Clinical Laboratory Measurements**

Hematology Panel	Blood Chemistry Panel	Others
HGB HCT Red blood cell (RBC) count Platelet count White blood cell (WBC) count WBC differential (neutrophils, lymphocytes, monocytes, eosinophils, basophils and reticulocytes) MCV	ALT, AST Gamma-glutamyl transferase (GGT) NT-proBNP or BNP Alkaline phosphatase (ALP) Amylase Lipase Total bilirubin Albumin Total protein Electrolytes (Potassium, Sodium, Calcium, Chloride) Lactate dehydrogenase (LDH) Blood urea nitrogen (BUN) Creatinine Glucose Iron Transferrin Thyroid stimulating hormone (TSH), FT4 Uric acid Low-density lipoprotein (LDL) High-density lipoprotein (HDL) Total cholesterol Triglycerides	Coagulation tests: PT-INR, aPTT, Fibrinogen Urinalysis (pH, blood, protein, glucose, WBC, nitrite) Urine beta 2 microglobulin Pregnancy test (urine) Serology: HBsAg, HCV antibody, HIV antibody Autoimmune markers: Antinuclear antibodies, TgAb, TPOAb Genetic test: JAK-2

Increases in liver enzyme levels in blood serum have been observed in subjects treated with pegylated IFNs. Therefore, liver enzyme levels (ALT, AST, and GGT) and total bilirubin will be measured at screening and subsequently, every 2 weeks in the treatment period of the trial, as well as at early withdrawal/EoT and the safety follow-up visit (if applicable). If the increase of liver enzyme levels is progressive and clinically significant, despite dose reduction, or is accompanied by increased total bilirubin, the subject will be withdrawn from the study.

Immunogenicity assessment of anti-P1101 antibodies (anti-drug antibodies; ADA) will be measured before the first dose (Week 0), 7 days (168 ( $\pm 24$ ) hr) after the initial P1101 dose, Week 4, 12, 24, 36, and at End of Treatment (EoT; Week 52), and at the EoS/Follow-up visit (28 days after the final P1101 drug administration at the EoT visit). Presence of anti-PEG antibodies will be measured. A multi-tiered ADA testing approach will include assays for the following: anti-P1101 binding antibodies and a confirmatory assay, antibody titers, and P1101 neutralizing antibodies. Blood samples will be collected from the subject confirmed positive for P1101 ADA at EoS visit every three months (Week 64, 76, and 88) until ADAs return to baseline levels or up to 12 months (Week 104). (Appendix 3)

### 15.4 Appropriateness of Measurements

Platelets and WBCs at baseline (Visit 1), Months 3, 6, 9, and 12 will be evaluated by a central laboratory.

Quantitative JAK2 allelic burden measurements will be also done by a central laboratory, every 3 months including baseline (Visit 1; Day 0).

## 16 SAFETY REPORTING

Clinical events occurring before starting study treatment but after signing the informed consent are recorded on the Medical History/Current Medical Conditions eCRF page.

### 16.1 Adverse Events

An adverse event (AE) is any untoward medical occurrence in a subject or clinical trial subject administered a medicinal product and which does not necessarily have a causal relationship with this treatment. All AEs occurring during the course of the clinical trial (i.e., from signing the informed consent form onwards through the treatment phase until the safety follow-up visit) will be collected, documented, and reported by the Investigator. Details on AE collection will be available in the eCRF collection guideline.

All AEs, serious and non-serious, will be fully documented on the appropriate eCRFs. For each AE, the Investigator will provide the onset, end, intensity, treatment required, outcome, seriousness, and action taken with the study drug. The Investigator will determine the relationship of the investigational drug to all AEs and record it in the eCRF. When assessing whether an AE is causally related to the study drug, the Investigator should consult the IB and use his/her clinical judgement and the subject's underlying disease before rendering an assessment.

All collected AEs will be coded according to the Medical Dictionary for Regulatory Activities (MedDRA). AEs and laboratory parameters will be graded according to CTCAE Version 5.0, (<http://ctep.cancer.gov>).

Adverse event monitoring should be continued until the safety follow-up visit/EoS or until AE resolution/stabilization, whichever occurs first. Safety follow-up visit is 28 days after end of treatment visit. AEs will be regarded as treatment-emergent if the time of onset or worsening is after or on the first intake of study drug.

Disease progression of PV should not be regarded or reported as an AE unless it is associated with a separate AE. Relationship will be assessed with not related, unlikely related, possibly related, probably and definitely related. Action taken will be described as dose increased, dose not changed, dose reduced, drug interrupted, drug withdrawn, and unknown.

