## 8.1 Disease Progression/Withdrawal Criteria

The reason(s) for a subject discontinuing from the study will be recorded in the electronic case report form (eCRF). A discontinuation occurs when an enrolled subject ceases participation in the study, regardless of the circumstances, prior to completion of the protocol planned schedule. The Investigator must determine the primary reason for discontinuation.

Discontinuation from the study may occur for the following reasons:

- Disease progression;

For this study, disease progression will be defined as:

- Death due to any cause
- Development of secondary MF, as evidenced e.g. by bone marrow biopsy
- Transformation into acute myeloid leukemia or myelodysplastic syndrome, as evidenced by bone marrow biopsy

- Screening failure;
- Withdrawal of patient consent;
- Severe Noncompliance;
- Worsening of the underlying disease in cases when the further participation (with dose adjustment) is not expected to provide sufficient medical care to the patient;
- Study drug-related adverse event (AE) not recovering within the pre-specified period\*;
  - pre-specified period\*: 8 weeks after discontinuation of IMP administration
- Medical condition unrelated to the underlying disease or study treatment (study drug-unrelated AE);
- Lost to follow-up.

The EoT visit will be performed at the time of study discontinuation.

In case of early treatment discontinuation, the subject should be invited to attend the safety follow-up visit (28 days after the EoT visit).

Subjects who discontinue study drug due to a study drug-related AE or abnormal laboratory value must be followed at least once a week for 8 weeks (and subsequently at 2-week intervals) until resolution or stabilization of the event. If a subject has not recovered from any toxicity within 8 weeks of prematurely discontinuing study drug, s/he must be discontinued from the study, but will continue to be followed for toxicity as described above. In this case, data will not be entered into the database but will be documented in the study log, which is stored at the site.

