## 16.6 Serious Adverse Events

Information about all SAEs will be collected and recorded on the AE eCRF page. To ensure subject safety, each SAE must also be reported to the Sponsor within 24 hours of learning of its occurrence. All SAE will be followed until resolution or up to 30 days following the last infusion / last dose of study drug. An SAE is defined in general as an untoward (unfavorable) event that is serious and has the following outcome(s):

- Death
- Life-threatening: The study subject's life was in an immediate danger due to the event.
- Hospitalization: The study subject had to be hospitalized due to the event.
- Prolongation of hospitalization: The existing hospital stay had to be prolonged due to the event.
- Persistent/significant disability/incapacity: The event resulted in persistent/ significant disability/incapacity having caused long-term changes (either anatomical, physiological, or psychic) affecting the study subject's life.
- Congenital anomaly/birth defect: Any abnormalities in features or functions of the offspring of the study subject who has been exposed to study drug treatment during pregnancy.

- Important medical event: The event is considered medically significant, but none of the above categories are applicable (e.g., the study subject required medical intervention to prevent the event to become life-threatening). Important medical events are those which may not be immediately life-threatening or result in death or hospitalization but may jeopardize the subject or may require intervention to prevent one of the other outcomes listed above.

Hospitalizations occurring under the following circumstances are not considered SAEs: admission to a hospice for respite care; hospitalizations planned before entry into the clinical study; hospitalization for elective treatment of a condition unrelated to the studied indication or its treatment; hospitalization on an emergency, out-subject basis that does not result in admission (unless fulfilling the criteria above); hospitalization as a part of the normal treatment or monitoring of the studied indication; and hospitalization not associated with any deterioration in condition.

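### Protocol 16.1 keeps disease progression out of AE reporting, in unresolved conflict with the SAE rules, so a transformation could be missing from the safety tables

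*Protocol*

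**What the plan says.** Protocol 16.1 sets the exclusion: "Disease progression of PV should not be regarded or reported as an AE unless it is associated with a separate AE".

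Protocol 8.1 supplies the meaning of the term. It opens with "For this study, disease progression will be defined as" and gives three components: "Death due to any cause", "Development of secondary MF, as evidenced e.g. by bone marrow biopsy" and "Transformation into acute myeloid leukemia or myelodysplastic syndrome, as evidenced by bone marrow biopsy". The synopsis carries the same list. Worsening of the underlying disease that makes further participation inadequate is a separate withdrawal reason in 8.1, outside this definition.

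Protocol 16.6 says "An SAE is defined in general as an untoward (unfavorable) event that is serious" and has one of several listed outcomes, of which death is the first. It adds: "Information about all SAEs will be collected and recorded on the AE eCRF page". Section 16.7.1 requires each SAE to reach the sponsor within 24 hours, whether or not it is thought to be related to treatment.

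Protocol 16.2 asks that clinically significant laboratory abnormalities be recorded as AEs if they lead to discontinuation or call for diagnostic evaluation, with a clinical diagnosis where possible.

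SAP 3.8 defines an AE as an event entered on the AE page of the eCRF, and an SAE as an AE reported as serious. The summary tables named in SAP 4.3.6.1 are all built from AEs, including the count of AEs leading to death. That section also defines on-study deaths but names no table or listing of them.

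**The concern.** An exclusion of progression from AE reporting is usually meant for expected worsening of the disease under study. Here the only definition of progression in the protocol contains none of that. It consists of the gravest outcomes: death, fibrotic transformation and leukaemic or myelodysplastic transformation. The exclusion therefore falls on the events for which a safety report most needs a complete count.

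These are not remote concerns in this setting. Protocol 5.1 names MF and secondary AML as long-term risks of PV. Section 5.3 reports that two cases of acute leukaemia in the earlier extension study were assessed as related to the comparator treatment, so causality was considered for such events before. Section 5.6 says that this study will support a marketing application in Japan. If sites record the same kind of event differently, the safety tables depend on how each site reads 16.1.

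**Working it through.** The documents give no figure on this point to reproduce. The check sets the sections side by side and follows four kinds of event through them.

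1. **Death from a distinct cause, such as stroke.** This is progression under 8.1. The stroke is a separate AE, so the exception in 16.1 applies. It is also an SAE under 16.6. The event is captured.

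2. **Death with no separate AE recognised** (unexplained, or attributed to the disease). This is progression under 8.1 and is excluded by 16.1 read literally. Under 16.6 death is an SAE outcome, and 16.7.1 requires a report within 24 hours. The two rules conflict, and nothing says which prevails.

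3. **AML or MDS found after abnormal blood counts.** This is progression under 8.1. Section 16.2 would put the laboratory abnormality on the AE page, with the diagnosis where possible. Section 16.1 says that progression is not an AE unless a separate AE goes with it. Whether the abnormal counts are a separate AE or simply the progression itself is left to the site.

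4. **Secondary MF found on an optional marrow sample, with no laboratory change that triggers 16.2.** This is progression under 8.1 and is excluded by 16.1. Section 16.6 brings it in only if it is judged to meet a seriousness criterion, for example as an important medical event. This is the weakest point of capture.

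**From collection to analysis.** Suppose a site follows 16.1 in cases 2 to 4 and makes no AE entry.

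- By SAP 3.8 the event is then neither an AE nor an SAE in the analysis.
- It cannot enter the SAP 4.3.6.1 tables, including the count of AEs leading to death.
- Under Protocol 16.1 causality is assessed for AEs, so none is recorded.
- Under 16.7.1 the 24-hour duty attaches to SAEs, so it may not be triggered.
- The AESI route does not clearly help. The examples in Protocol 7.4 and SAP 2.3.3 are cardiovascular, haemorrhagic, thrombotic and psychiatric events, and SAP 3.8 again takes AESIs from the AE page.
- The event remains visible as a reason for discontinuation (SAP 4.3.2) and in the listings of all database data (SAP 4.3.1). In 8.1 progression is a single withdrawal reason, so a disposition table built on that list would not by itself separate a death from a transformation.

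**Size of one omission.** The input is the planned 30 patients (synopsis), with exact Clopper–Pearson 95% intervals.

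- Recorded, 1/30: the rate is 3.3%. The lower limit is 1 − 0.975^(1/30) = 0.08%. The upper limit solves (1 − p)^30 + 30p(1 − p)^29 = 0.025, giving p = 17.2%.
- Omitted, 0/30: the rate is 0%, with upper limit 1 − 0.025^(1/30) = 11.6%.

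**The case against.** The strongest reply is that other rules already catch most of these events, and much of it stands.

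- **Deaths.** Section 16.6 lists death without any exception for progression. The circumstances it does exempt from SAE status are all kinds of hospitalisation. Many deaths would also come with a separate AE. A reader might infer that any death can drop out of the safety data. The documents do not support that: the exposure is limited to deaths with no separate AE, and even there 16.6 and 16.7.1 point towards reporting.
- **Transformations.** Section 16.2, and 16.3 for physical findings, may bring some of them onto the AE page with a diagnosis. The overlap is real but incomplete, since neither section says how it relates to the exclusion in 16.1.
- **Data retention.** A reader might infer that the events would vanish altogether. They would not, because SAP 4.3.1 lists all database data and 8.1 records discontinuation reasons in the eCRF. What is at risk is the AE and SAE tables, the causality assessment and the expedited report.
- **Unseen guidance.** Section 16.1 refers to an eCRF collection guideline, which may settle the matter in practice. It is not among the documents available here. Even if it does, the protocol text should not contradict it.

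The reply narrows the point. It does not remove it, because no section ranks 16.1 against 16.6.

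**Conclusion.** The point holds as an unreconciled conflict between 8.1 with 16.1 on one side and 16.6 with 16.7.1 on the other, with 16.2 sitting uneasily beside both. It is strongest for secondary MF, AML and MDS, and weaker for deaths. The text shows that such an event could be absent from the AE and SAE tables, not that it will be.

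This rests on two assumptions: that a site reads 16.1 literally with the study's own definition of progression, and that no guidance outside these documents overrides it. The documents give no expected rate of transformation. In a 12-month study of 30 patients the number is probably small, but one omission is enough to change a reported 3.3% to zero. The primary analysis and the sample size are unaffected. The correction should be made because a stated rule, and not merely a missing detail, can produce a wrong safety result.

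**What to change.** **Protocol.** Reconcile 8.1, 16.1 and 16.6. Add a sentence to 16.1 stating that the exclusion does not cover death, secondary MF, MDS or AML, or alternatively that 16.6 prevails over 16.1. Either way, these events should be recorded on the AE page with a causality assessment, and reported as SAEs when they meet 16.6. Check that the eCRF collection guideline agrees.

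**SAP.** Add to 4.3.6.1 a listing of all deaths and all progression events by type (secondary MF, MDS, AML), whatever their AE status.

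**Cost.** One protocol sentence and one listing. The endpoints, sample size and primary analysis do not change. If patients have already been treated, sites should also check recorded discontinuations for progression against the AE page.
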